6.12.5 Unsatisfactory long-term clinical response

Only subjects who have been on treatment for at least 24 weeks are eligible for meeting this definition. In order to declare unsatisfactory long-term clinical response, a subject must meet the 6MWT decrement criterion and show lack of sustained improvement in WHO functional class. Similar to disease progression, a subject must attend two study visits for 6MWT measurements: initial test and confirmatory test. Any unsatisfactory long-term clinical response that occurs from randomization to the subject's last study visit is counted as an event for the primary outcome. The date of the event is the actual date of unsatisfactory long-term clinical response (initial 6MWT test). All those without a reported unsatisfactory long-term clinical response up to their last visit are censored for unsatisfactory long-term clinical response at the last study visit.

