2 STUDY OBJECTIVES

2.1 Primary Objective

The primary objective of this study is to compare the effect of esuberaprost (BPS-314d-MR) to placebo, each added to treprostinil, inhalation solution (Tyvaso®) on the composite endpoint of time-to-clinical-worsening (TtCW), defined as the time from randomization to the first of any of the following clinical worsening events:

- Death (all causes)
- Hospitalization due to worsening pulmonary arterial hypertension (PAH), defined as:
 - Non-elective hospitalization lasting at least 24 hours in duration caused by clinical conditions directly related to PAH and/or right heart failure and requiring intensification of treatment; or Lung or heart/lung transplantation; or Atrial septostomy
- Initiation of a parenteral (infusion or sub-cutaneous) prostacyclin directly related to worsening PAH (transient use [\leq 7 days] for non-PAH related illness allowable)
- Disease progression (all criteria below required):
 - A decrease in six minute walk distance (6MWD) of at least 15% from Baseline (defined as the average of the two 6MWTs performed on sequential days of the Baseline Visit), or being too ill to walk as a consequence of PAH progression, confirmed by six-minute walk tests (6MWT) performed at 2 consecutive visits,
 - Worsening of PAH symptoms, which must include either:
 - An increase in WHO Functional Class or
 - Worsening symptoms of right heart failure
- Unsatisfactory long-term clinical response (all criteria below required):
 - Receiving randomized treatment for at least 24 weeks
 - A decrease of at least 15% from Baseline (defined as the average of the two Baseline Visit 6MWTs) in 6MWD, or too ill to walk, directly related to PAH progression, at Week 24 and beyond; at 2 consecutive visits, and
 - Sustained WHO Functional Class III or IV symptoms for at least 24 weeks.

The Investigator will use the above criteria to provide an initial judgment of whether a suspected clinical worsening event has occurred. A blinded Event Adjudication Committee (EAC) will review all suspected clinical worsening events and make a final determination for each (see [Appendix 1](#)).

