2.2 Secondary Objectives

The study protocol lists the following secondary objectives:

- To compare the effect of esuberaprost (BPS-314d-MR) and placebo each added to inhaled treprostinil on the composite endpoint of time-to-clinical-failure (TtCF), defined as the time from randomization to the first of any of the following events:
 - Meets primary endpoint definition of clinical worsening, as confirmed by the EAC; or
 - Receiving randomized treatment for at least 24 weeks and has:
 - Lack of sustained improvement from Baseline WHO Functional Class, defined by two consecutive visits of no sustained improvement from Baseline WHO Functional Class where visits may be scheduled or unscheduled and
 - Lack of sustained improvement from the Baseline 6MWT (average at Baseline), defined by two consecutive visits of no sustained improvement from Baseline 6MWT (≤ 0 meters or too ill to walk, directly related to PAH); visits may be scheduled or unscheduled.
- To compare the effects of BPS-314d-MR to placebo on changes from baseline to each scheduled study visit, as applicable, for the following measures:
 - 6MWT
 - Borg Dyspnea Score
 - WHO Functional Class
 - N-terminal pro-brain natriuretic peptide (NT-pro-BNP) levels
- To evaluate the safety of BPS-314d-MR based on adverse events (AEs), clinical laboratory parameters, electrocardiogram (ECG) findings, physical examination, and vital signs.

The section for Efficacy and Safety Endpoints (Section 5) present explicitly-defined secondary endpoints (rather than general protocol-specified objectives).

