3 STUDY DESIGN

3.1 General Description

This Phase 3, multicenter, double-blind, randomized, placebo-controlled study is designed to assess the efficacy and safety of oral esuberaprost in subjects with PAH who are also treated with treprostinil, inhalation solution (Tyvaso). The study, which is initiated and sponsored by Lung Biotechnology PBC, formerly known as Lung LLC and Lung Biotechnology Inc. (sponsor), is being performed at study centers within the US and Israel.

The subject population includes males and females 18 to 80 years, inclusive, with a diagnosis of PAH that is either idiopathic or familial, collagen vascular disease associated PAH, PAH associated with HIV infection, PAH induced by anorexigens/toxins, or PAH associated with repaired congenital systemic-to-pulmonary shunts (repaired ≥ 1 years). For randomization, subjects must be WHO Functional Class III or IV and have declining or unsatisfactory clinical response to inhaled treprostinil therapy. The protocol defines unsatisfactory clinical response as having at least 90 days of uninterrupted inhaled treprostinil treatment, in which a stable dose of inhaled treprostinil has been received for at least 30 days prior to baseline/randomization, and still meeting the clinical criteria of a moderately-to severely-ill PAH patient, described in the protocol-defined inclusion/exclusion criteria. Subjects are permitted to receive other approved PAH therapies of an optimal, stable dose regimen for at least 30 days prior to the Baseline Visit and maintained throughout the study. Patients must sign informed consent prior to participation in any study procedure.

After the Screening Visit, subjects who consent to the study and are determined to be eligible but are not currently taking inhaled treprostinil will enter a run-in period on inhaled treprostinil to achieve 90 days of experience in order to ensure drug tolerability before being randomized.

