6.12 Primary Efficacy Analysis

As described in Section 2.1, the primary efficacy outcome is the TtCW, measured in days, where clinical worsening is defined as the first occurrence of any of the following:

- Death (all causes)
- Hospitalization due to worsening PAH
- Initiation of a parenteral (infusion or sub-cutaneous) prostacyclin directly related to worsening PAH
- Disease progression

- Unsatisfactory long-term clinical response

As described above, a blinded Event Adjudication Committee (EAC) will review all suspected clinical worsening events and make a final determination for each (see [Appendix 1](#)). The EAC Charter, Version [REDACTED], specifies evidence to be provided to the EAC along with the general rules and criteria for EAC confirmation of a primary endpoint of clinical worsening. Because the EAC Charter cannot address every possible scenario, the EAC Charter shall be viewed as a framework under which the EAC will operate. Each case will be determined on the basis of a consensus of the EAC, the members of whom are independent experts in PAH. Please see [Appendix 2](#) for general rules and criteria excerpted from the EAC Charter.

Subjects were not required to discontinue from the study after meeting a primary endpoint; thus, more than one clinical worsening event may be reported for the same subject. This section defines the calculation of time to each component of the primary outcome. The protocol specifies that investigators follow each subject for 30 days after the subject discontinues from the study to assess the occurrence of SAEs and for 90 days after the subject stops study medication for vital status. Further, the investigators are instructed to provide all clinical worsening events that occur after the primary clinical worsening event, as well as the vital status of all subjects at the time the sponsor terminates the study.

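### SAP 6.12.5 gives a WHO-class criterion for the long-term-response component of the primary endpoint that contradicts SAP 2.1 and the protocol

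*SAP*

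**What the plan says.** SAP 2.1 defines this component by three criteria that must all be met: at least 24 weeks of randomized treatment; a walk criterion, "A decrease of at least 15% from Baseline (defined as the average of the two Baseline Visit 6MWTs) in 6MWD, or too ill to walk", at two consecutive visits from Week 24 on; and a functional-class criterion, "Sustained WHO Functional Class III or IV symptoms for at least 24 weeks". Protocol 2.1 and 7.10.1 carry the same class criterion.

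SAP 6.12.5 restates the component. It keeps the treatment requirement: "Only subjects who have been on treatment for at least 24 weeks are eligible for meeting this definition". It refers to the walk criterion in short form. For functional class it says the subject must "show lack of sustained improvement in WHO functional class".

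Similar wording appears in SAP 2.2, for the secondary endpoint of time to clinical failure: "Lack of sustained improvement from Baseline WHO Functional Class, defined by two consecutive visits of no sustained improvement from Baseline WHO Functional Class".

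On the role of Section 6.12, the SAP says: "This section defines the calculation of time to each component of the primary outcome". On who decides, it says the EAC "will review all suspected clinical worsening events and make a final determination for each". SAP 5.1.1 computes time to clinical worsening from the date of the first EAC-confirmed event and points to Section 2.1 for the definition.

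**The concern.** The two class criteria measure different things. SAP 2.1 asks whether the subject has stayed in Class III or IV for 24 weeks. SAP 6.12.5 asks whether the subject has failed to hold an improvement. It sets no class level and no duration for class, does not say what 'sustained' means, and does not name the reference class, although baseline is the natural reading.

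The difference matters because this is a component of the primary endpoint. It feeds the first-event date in SAP 6.12.6 and is analyzed separately as an incidence outcome under SAP 6.12.7. Both criteria sit in the SAP, and no text says which one governs. SAP 6.12.4, by contrast, abbreviates the disease-progression criteria without changing the rule.

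**Working it through.** No figure in the plan depends on this wording, so the check sets the two rules side by side and applies both to the same subjects.

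**Inputs**
- Baseline class: for randomization, "subjects must be WHO Functional Class III or IV" (SAP 3.1).
- Visits: the quarterly visits, taken as Weeks 12, 24 and 36. Weeks 12 to 36 span 36 − 12 = 24 weeks.
- Held constant: the walk criterion and the 24 weeks of treatment are taken as met, and no other component has occurred earlier.
- Rule A (SAP 2.1): Class III or IV at every one of these visits.
- Rule B (SAP 6.12.5): no sustained improvement from baseline. Because 'sustained' is undefined there, two readings of a sustained improvement were tried: better than baseline at the last two visits, or better than baseline at all three.

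**Results** (Rule B gives the same answer under both readings in every row)

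| Baseline | Weeks 12 / 24 / 36 | Rule A (2.1) | Rule B (6.12.5) |
|---|---|---|---|
| III | III / III / III | event | event |
| III | IV / IV / IV | event | event |
| IV | IV / IV / IV | event | event |
| IV | III / III / III | event | not an event |
| III | III / II / III | not an event by Week 36 | event |

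**Row 4.** The subject has never left Class III or IV, so 2.1 is met. The subject has also held a one-class improvement throughout, so 6.12.5 is not met.

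**Row 5.** The Class II visit at Week 24 breaks the run of Class III or IV before it reaches 24 weeks, so 2.1 is not met by Week 36. The improvement was not held, so 6.12.5 is met. If the subject then stays in Class III, 2.1 could be met from Week 36 + 24 = Week 60. The two rules may therefore differ on when the event can be declared and not on whether it ever is. Whether the recorded date would also move is not clear, because 6.12.5 dates the event at the initial walk test.

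All 4 × 4 × 4 = 64 class paths were then run for each baseline class. Paths that count only under 2.1 arise only for Class IV entrants: III/III/III and IV/III/III under the first reading, III/III/III alone under the second. Paths that count only under 6.12.5 arise for both baseline classes under both readings. These are possible paths, not probabilities, and they say nothing about frequency.

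**Does another component catch these subjects?** Disease progression needs the walk decline plus either an increase in functional class or worsening symptoms of right heart failure. In rows 4 and 5 the class is at or below baseline at every visit. If the increase is read as from baseline, the class route is closed. Unless right-heart-failure symptoms worsen or another event occurs, the long-term-response component decides whether these subjects count.

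**The case against.** The strongest reply is that 6.12.5 is shorthand. Section 6.12 opens by referring to 2.1, and 6.12.5 mainly sets the event date and the censoring date. It abbreviates the walk criterion too, with no 15% and no mention of being too ill to walk. The EAC decides every suspected event, and the endpoint uses EAC-confirmed dates. On this view a loose paraphrase changes nothing.

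Much of this stands, and it rules out two stronger readings that a reader might infer.

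- *That a component programmed by the sponsor will disagree with the adjudicated one.* The documents describe no such programmed event status for clinical worsening. SAP 5.1.1 uses EAC-confirmed dates, and protocol 7.10.2 says that the sponsor derives clinical failure from the data, in contrast to clinical worsening.
- *That 6.12.5 overrides the protocol because the SAP supersedes its statistical considerations.* SAP 2.1 itself keeps the protocol criterion. The conflict lies inside the SAP, and precedence over the protocol cannot settle it.

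It is also only an inference that the 6.12.5 wording came from the clinical-failure endpoint; it omits that endpoint's reference to baseline and its two-visit rule.

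What does not stand is that the text is harmless. Abbreviating the walk criterion refers back to 2.1, whereas the class wording puts a different rule in its place, in a sentence that says what is needed to declare the event. EAC authority limits the consequence but does not show which rule was applied: SAP 6.12 treats the charter as a framework, and its excerpt is not readable in the public copy. If the EAC follows 2.1, then 6.12.5 misdescribes the endpoint. If it follows 6.12.5, the endpoint departs from the protocol.

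**Conclusion.** The point holds as a contradiction between two statements of one primary-endpoint criterion. The rules give opposite answers for a subject who improves from Class IV to a lasting Class III. They can differ in status or timing for a Class III subject with a passing Class II visit. They agree for subjects who stay in Class III or IV without improving.

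The number of affected events cannot be stated and is probably small. Disagreement needs an improvement in class, lasting or passing, together with a walk decline of at least 15% (or being too ill to walk) at two consecutive visits, and no earlier event of another kind. A reader might try to size the problem by the number of Class IV entrants. The documents do not give that share, and it would count everyone exposed to the conflict, not those whose classification changes. No effect on the 113 planned events or on power can be computed.

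The disagreement turns on improvement in functional class, which treatment may affect, so it need not fall equally on the two arms. The documents do not allow a net direction to be stated.

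This rests on reading the reference class in 6.12.5 as baseline and on the EAC charter rule being unknown here.

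**What to change.** Before unblinding:

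1. Reconcile the two SAP sections by making 6.12.5 cite SAP 2.1 for the class criterion, or repeat the SAP 2.1 and protocol criterion verbatim.
2. State what 'sustained' means in terms of visits: which visits count, whether unscheduled visits count, and whether a single visit below Class III restarts the 24 weeks. Copying the 2.1 wording alone would leave this open.
3. Confirm that the EAC charter applies the same rule. If it does not, review the events adjudicated under this component while still blinded.

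The first step is one sentence and the second a few more. The SAP already provides for addenda before unblinding (6.2 and 6.12.6), which can carry both. The third is a document check, with further work only if a difference is found.

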6.12.6 First Occurrence Derivation and Analysis

Each subject will be assigned responses for each component of the primary efficacy endpoint. The response will be either the date the event occurred or the date of censoring. Then, the subject will receive one date as the outcome. For subjects who experience at least one of the component outcomes, the event date will be the earliest of the dates of the component outcomes. For those who do not experience any of the outcomes, the date of censoring will be the date of the last study visit.

Prior to unblinding, an addendum will describe in detail the methods to be used to account for missing data in the analysis of the primary outcome.

The TtCW (in days) will be analyzed using the SAS procedure LIFETEST to calculate the log-rank statistic and the associated p-value for testing whether the treatment groups differ. The program will be of the form:

```
proc lifetest data= set plots=survival;
  time TtCW * status(0);
  strata treprostинil_use / group=treatment test=logrank;
  run;
```

The results of the statistical test for the primary study endpoint will be evaluated using a two-sided Type I error rate of 5%. A Cox Proportional Hazards Model (SAS PHREG) will be used to estimate the hazard ratio and its associated 95% confidence interval (CI). This model

will stratify by baseline treprostinil. Graphical displays and tabulations of TtCW will be presented by treatment group.

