6.12.1 Death (All Cause)

Deaths that occur at any time from randomization to 90 days after the subject's last study visit is counted as a death for the primary efficacy analysis. All those still alive 90 days after their last visit are censored for death at the 90 day time even if it is known that they died after the 90 day window.

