6.12.2 Hospitalization due to worsening PAH

Any hospitalization due to worsening PAH that occurs from randomization to the 30 days following subject's last study visit is counted as an event for the primary outcome. The date of the event is the actual date of hospitalization. All those without a reported hospitalization during the 30 days following their last visit are censored for hospitalization at the 30 day time even if it is known that they were hospitalized after the 30 day window.

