6.12.3 Initiation of a Parenteral (infusion or sub-cutaneous) Prostacyclin

Any initiation of a parenteral prostacyclin, directly related to worsening PAH (transient use [≤ 7 days] for non-PAH related illness allowable, that occurs from randomization to the 30 days following subject's last study visit is counted as an event for the primary outcome. The date of the event is the actual date of transition to parenteral prostacyclin. All those without a reported parenteral prostacyclin during the 30 days following their last visit are censored for parenteral prostacyclin at the 30 day time even if it is known that they received parenteral prostacyclin after the 30 day window.

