6.12.4 Disease Progression

Disease progression is assessed at each study visit. In order to declare disease progression, a subject must meet the 6MWT decrement criterion and worsening of PAH symptoms. To satisfy the 6MWT criterion, subject must attend two study visits for 6MWT measurements: initial test and confirmatory test. Any disease progression that occurs from randomization to the subject's last study visit is counted as an event for the primary outcome. The date of the event is the actual date of disease progression as defined by the initial 6MWT test. All those without a reported disease progression up to their last visit are censored for disease progression at the last study visit even if it is known that disease progression occurred after the last study visit.

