6.12.7 Supportive Analyses for Primary Analyses

Two distinct analyses will be performed for the components of the primary outcome.

1. “Contribution” outcome. A table will show the contribution of each component of the primary outcome.
2. “Incidence” outcome. Each component will be analyzed as a time-to-event variable.

These two analyses differ in that the analysis of the contribution shows only the first event in the primary outcome while the second considers the time to each component even if it is not the first event in the primary. For example, a subject who dies after experiencing disease progression would not show as a death in the analysis of the contribution of the component; however, the death of such a subject would be included in the second analysis.

Analysis of the “contribution” outcome will be descriptive. It will consist of a simple table showing the number of events of each type by treatment group contained in the primary outcome.

For the “incidence” outcomes, LIFETEST and PHREG will be used for each of the five individual components of the composite outcome. These analyses will use the component-specific dates of event or censoring. They will produce Kaplan-Meier curves, hazard ratios, 95% CIs, and other statistics as appropriate.

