6.12.8 Sensitivity Analyses for the Primary Outcome

In addition to the primary and supportive analysis, two planned sensitivity analyses will be performed.

The first sensitivity analysis will mimic the methods Sitbon et al (2015) used in their primary analysis of selexipag in the GRIPHON study. As those authors say, “The primary analysis was an on-treatment analysis with follow-up data censored at the time selexipag or placebo was discontinued.” The first sensitivity analysis will follow this method and censor subjects at the time they stopped study medication.

The second sensitivity analysis, which is really a set of analyses, will explore the impact of censoring and missing data. These analyses will use a tipping point approach, in which subjects will be censored at Day 1, Day 2, ..., Day 90 after stopping study medication in order to explore the effect of various censoring rules on the inference from the study.

Because of the complexity of the primary and secondary outcomes, and the many possible ways that data might be censored or missing, the statistical team will examine the pattern of missing data and censoring for the pooled efficacy variables at the time of the Blind Data Review (see Section 6.11). At that point, armed with the knowledge of the patterns of divergence from full follow-up that actually occur in the trial, the sponsor may add additional sensitivity analyses, which will be described in an addendum to this SAP (completed prior to database lock).

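### Primary TtCW: time after the last study visit counts only if it ends in an event, because SAP 6.12.6 censors event-free subjects at the visit; the effect is small, but the rule is wrong as written

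*SAP*

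**What the plan says.** SAP 6.12.1 to 6.12.5 give each component of the composite its own window and censoring date.

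- **Death (6.12.1).** "Deaths that occur at any time from randomization to 90 days after" the last study visit are primary events. For survivors: "All those still alive 90 days after their last visit are censored for death at the 90 day time".
- **PAH hospitalisation (6.12.2).** Counted to 30 days after the last visit. "All those without a reported hospitalization during the 30 days following their last visit are censored for hospitalization at the 30 day time".
- **Parenteral prostacyclin (6.12.3).** Also counted to 30 days. Subjects without a start "are censored for parenteral prostacyclin at the 30 day time".
- **Disease progression (6.12.4).** Counted only to the last visit. Subjects without it "up to their last visit are censored for disease progression at the last study visit". Unsatisfactory long-term response (6.12.5) is treated the same way.

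SAP 6.12.6 then builds the composite. A subject with any component event takes the earliest component date, which may fall after the last visit. For everyone else: "For those who do not experience any of the outcomes, the date of censoring will be the date of the last study visit".

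The component censoring dates are kept for the incidence analyses in 6.12.7: "These analyses will use the component-specific dates of event or censoring". They do not reach the primary composite. SAP section 1 states that the SAP replaces the protocol's statistical section, so 6.12.6 is the operative rule.

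**The concern.** Log-rank and Cox methods require that whether a stretch of time is at risk does not depend on how it ends. Here it does. Take two subjects whose last visit is day 100. One dies on day 170, stays in the risk set to day 170 and counts as an event. The other is known to be alive on day 190, yet leaves the risk set on day 100. The 70 days before the death are counted; the 90 event-free days are not.

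Post-visit events thus enter with too little matching risk time, which pushes the estimated event rate up in any arm with leavers. If both arms lose subjects equally, the treatment comparison is nearly untouched, but both Kaplan-Meier curves run high. If one arm loses more, the comparison tilts against that arm: conservative if it is the active arm, favourable to active if it is placebo.

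TtCW carries the trial's main claim and is the gate to all secondary testing (SAP 6.10.1). TtCF in 6.13.2 counts clinical worsening and refers back to the TtCW approach for censoring at the last study visit, so it inherits the problem. Total mortality in 6.14.5 does not: it censors subjects lost to follow-up at the date they were last known alive.

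**Working it through.** **Design figures first.** The one-year rates in SAP 4.1 are 45% (placebo) and 25% (active). Hazards: −ln(0.55) = 0.598 and −ln(0.75) = 0.288 per year. HR = 0.288/0.598 = 0.481. Schoenfeld events for 90% power at two-sided 0.01: 4(2.576 + 1.282)²/(ln 0.481)² ≈ 111.2, so 112 against the stated 113. With 113 events, power is 90.5% at 0.01 and 97.3% at 0.05, against the stated 90% and 97%. The design is reproduced.

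**Inputs for the censoring rule.**

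- From the documents: 120 per arm, accrual 1.5 years, total 2.5 years (SAP 4.1); SAE capture to 30 days after the last visit (Protocol 7.12.2); vital status three months after discontinuation, or at study conclusion if sooner (Protocol 7.14); about 20% premature termination in other PAH studies (SAP 6.4.2).
- Assumed: null hazard 0.42 per year (1 − e^(−0.42) = 34% at one year, near the middle of 25% and 45%); event mix 20% death, 50% hospitalisation or parenteral start, 30% walk-based; withdrawal by arm as shown; last visit taken as end of participation.

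**How many post-visit events (null, withdrawal 0.2 per year in both arms).** The total exit rate is 0.42 + 0.20 = 0.62 per year and follow-up is uniform on 1 to 2.5 years.

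- Share still in and event-free at close: (e^(−0.62) − e^(−1.55))/(0.62 × 1.5) = 0.350, or 84 of 240.
- Events during participation: (0.42/0.62)(1 − 0.350) × 240 = 106.
- Early leavers: (0.20/0.62)(1 − 0.350) × 240 = 50, or 21%.
- Non-walk hazard: 0.7 × 0.42 = 0.294 per year. Chance of such an event within 30 days: 1 − e^(−0.294 × 30/365) = 0.0239.
- Further chance of death between days 30 and 90, at death hazard 0.2 × 0.42 = 0.084 per year: e^(−0.294 × 30/365) × (1 − e^(−0.084 × 60/365)) = 0.0134.
- Completers, 30 days: 84 × 0.0239 = 2.0. Leavers: 50 × (0.0239 + 0.0134) = 1.9. Total 3.9, slightly high because some leavers reach study close first. Simulation gives 3.8.
- If completers' deaths also count to 90 days, as 6.12.1 literally reads: 3.9 + 84 × 0.0134 = 5.0. If only half the leavers can be traced: 2.0 + 0.9 = 2.9. If completers have no post-visit window: about 1.8.

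**Effect on the analysis.** Simulation, 20,000 trials per null scenario (Monte Carlo error about 0.11 points at 2.5%) and 10,000 per design-alternative scenario, unstratified log-rank and Cox. Option (a) stops events and time at end of participation. Option (b) runs both to 30 days later for the non-walk components.

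| Scenario | SAP rule | Option (a) | Option (b) |
|---|---|---|---|
| Null, withdrawal 0.2 in both arms | HR 1.00; 2.2–2.5% per side | – | – |
| Null, active 0.3, placebo 0.1 | HR 1.02; 3.1% favour placebo, 2.0% favour active | HR 1.00; 2.4–2.6% per side | HR 0.99–1.00; 2.4–2.7% per side |
| Null, active 0.1, placebo 0.3 | HR 0.98; 3.0% favour active, 2.0% favour placebo | as above | as above |
| 45% vs 25%, equal withdrawal | power 96.9% | 96.3% | 96.8% |

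Kaplan-Meier event probability under the SAP rule with equal withdrawal is 34.7% at one year and 58.5% at two years, against true values of 34.3% and 1 − e^(−0.84) = 56.8%. On the literal 90-day reading the two-year figure is 59.1%. At the design alternative with 0.3 against 0.1 withdrawal, HR 0.48 becomes 0.49 if active leaves more and 0.47 if placebo does. With half the leavers traced, the null HR is 1.01 or 0.99, with 2.8% or 2.9% on the affected side.

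**Stress case.** If the hazard triples after leaving, the SAP rule gives HR 1.05 or 0.96. Following everyone to close would itself give 1.17 or 0.86, so this is no null for a treatment-policy question and no Type I error claim is drawn from it.

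**The case against.** The best case against acting is size. Summing both sides, the unequal-withdrawal nulls reject in 3.1 + 2.0 = 5.1% and 3.0 + 2.0 = 5.0% of trials, which is the nominal level. The hazard ratio moves by 0.01 to 0.02, and the documents give no withdrawal rates by arm. That stands, and it is why the effect is called small. What remains is a directional tilt of about half a point per side and a biased Kaplan-Meier curve.

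Second, SAP 6.12.8 already explores censoring. One analysis will "censor subjects at the time they stopped study medication", and another moves the cut-off from 1 to 90 days after drug stop. These would help show whether the result depends on the rule. But both are anchored to stopping medication rather than to the last visit, subjects may stay in the study off drug (SAP 6.4.2), and neither alters the primary p-value.

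Third, two addenda are promised before unblinding: data conventions (SAP 6.2) and missing data for the primary outcome (6.12.6). Their content is unknown. Either could carry the correction, but as the text stands the censoring date is a stated rule, not a gap left for them.

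Fourth, walk-based components can be seen only to the last visit, so that is the last date on which the full composite is known to be event-free. This is a sound argument for stopping there, but then events should stop there too.

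Fifth, about half of the 3.8 post-visit events come from completers. With early leavers only, the two-year Kaplan-Meier figure is about 57.5% rather than 58.5%. The simulation also closes at a fixed 2.5 years, whereas the trial ends at 113 events. Both points affect the size, not the error.

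**Conclusion.** The concern holds. As written, the primary composite uses different end dates for subjects with and without an event, which contradicts the component rules in the same section and makes censoring depend on outcome. No assumption is needed to see this.

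The size does rest on assumptions: withdrawal by arm, event mix, and hazard after leaving. Over the range examined, the rule adds about 2 to 5 post-visit events to about 106. It leaves the treatment comparison essentially unchanged under equal withdrawal, overstates two-year event probability by up to about 2 points, and shifts the hazard ratio by 1 to 2% under threefold unequal withdrawal with unchanged hazard. It would matter more if withdrawal were strongly unequal and closely tied to deterioration, though part of that shift comes from counting post-withdrawal events at all. The effect on TtCF was not quantified.

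This should be fixed: the effect is small, but it falls on the primary endpoint, can run in favour of the active drug, and is cheap to remove.

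**What to change.** In SAP 6.12.6, before unblinding, define one end-of-observation date per subject and use it both to count events and to censor. Two definitions are acceptable.

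- **(a) End of participation:** End of Study visit, withdrawal, or last contact if lost to follow-up. It should not be the last attended quarterly visit, so that events between visits while enrolled still count.
- **(b) End of participation plus 30 days,** or first open-label dose if earlier, for death, hospitalisation and parenteral start. Event-free subjects are censored at the end of that window, or at last contact within it. State that walk-based components cannot be observed after the visit.

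Make one primary and the other a sensitivity analysis. A 90-day end date for the composite would not work, because hospitalisations and parenteral starts are counted only to day 30.

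Apply the same date to TtCF in 6.13.2. Keep the component windows for the 6.12.7 incidence analyses and leave later deaths to 6.14.5. Define the last study visit, and reconcile 6.12, which runs the 90-day vital-status check from stopping medication, with 6.12.1, which runs it from the last visit.

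The cost is SAP wording and one derived date; (b) may also need the first dose date from the extension study. Option (a) drops the post-participation events, about 2 to 5 per trial, with 96.9 − 96.3 = 0.6 points less power at the design alternative. Option (b) keeps most of them, at 96.8%.
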